#### 9.5 Evaluability for Toxicity

A patient will be considered for toxicity monitoring if the patient is eligible, receives at least one dose of protocol therapy, and one of the following occurs: (1) completes a full cycle of therapy with no toxicities; (2) dies on protocol therapy for a reason considered possibly, probably, or likely related to protocol therapy; or (3) experiences an adverse experience possibly, probably, or likely related to one of the agents. A toxicity-evaluable patient will be considered in the analysis during the interval from study enrollment until protocol therapy is terminated or a toxicity-event is observed, whichever occurs first. A toxicity-evaluable patient will be considered to have experienced a protocol-specific toxicity event if: (1) the patient dies on protocol therapy for a reason considered possibly, probably, or likely related to protocol therapy; or (2) experiences a dose-limiting toxicity.

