#### 4.4.5 Immunosuppression

Unlike chemotherapy, LMP T cells do NOT provide any immunosuppression. Patients assigned to Arm LMP-TC are required to have minimum levels of either calcineurin inhibitors and/or MTOR inhibitors at the start of the course and must maintain these minimum levels throughout the course. To prevent organ rejection, compliance with the below guidelines is required.

MINIMUM Levels for Calcineurin inhibitors:

Tacrolimus 4 ng/ml

Cyclosporine 100 ng/ml

MINIMUM Levels for MTOR Inhibitors:

Sirolimus 4 ng/ml

Everolimus 3 ng/ml

For patients on combination therapy, the minimum level needs to be maintained at least for the calcineurin inhibitors.

Course LMP-TC2 will start as soon as a suitable LMP-specific T-cell product is available but no later than 21 days from the end of LMP-TC1.

See [Section 5.0](#) for Dose Modifications including management of infusion-related reactions.

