**7.1.2 Arm LMP-TC**

End of therapy is Day 42 of Course LMP-TC1 for patients with a CR or PD after this course and for patients with PR or SD after this course who do not have a suitable T-cell product available for Course LMP-TC2.

End of therapy is Day 42 of Course LMP-TC2 for all other patients.

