We will assess the proportion of successes for the primary aim on the first 15 patients assigned to Arm LMP-TC as an interim futility monitoring rule. If fewer than 10 of the first 15 patients are successes for the primary aim (matched and treated within the prescribed timeframe), the Study Committee will assess the reasons for failure and may choose to close the study if it is felt that the reasons are not correctable. If the true success rate is 60%, this rule will be invoked with probability 59.7%; if the true success rate is 80%, the rule will be invoked with probability 6.1%.

We will do real-time monitoring for progression rate at week 10 and for certain protocol-specific toxicities, namely: allograft failure, allograft rejection, cytokine release syndrome grade 3 or higher, and graft versus host disease (see [Appendix V](#)). The monitoring will be done using Bayesian rules with beta priors. The four parameters for each scenario are the two beta distribution parameters ( $\alpha, \beta$ ), the unacceptable probability rate for the event we are monitoring ( $p_0$ ), and the posterior probability that the actual rate exceeds  $p_0$  ( $P(p > p_0 | \text{Data})$ ), which is calculated using the standard Bayesian posterior probability formula

$$P(p > p_0 | \text{Data}) = \frac{\int_{p_0}^1 \binom{n}{x} p^x (1-p)^{n-x} \frac{\Gamma(\alpha + \beta)}{\Gamma(\alpha)\Gamma(\beta)} p^{\alpha-1} (1-p)^{\beta-1} dp}{\int_0^1 \binom{n}{x} q^x (1-q)^{n-x} \frac{\Gamma(\alpha + \beta)}{\Gamma(\alpha)\Gamma(\beta)} q^{\alpha-1} (1-q)^{\beta-1} dq},$$

where  $n$  is the number of observations and  $x$  is the number of events among those  $n$  observations.

We will suspend enrollment to the study if any patient suffers or is suspected to suffer allograft failure or allograft rejection to review the circumstances of the failure or rejection. A recommendation to re-open enrollment might be made if causes other than study therapy were thought to be the primary cause of failure or rejection.

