For cytokine release syndrome and graft versus host disease, the analytic unit for monitoring for protocol-specific toxicities will be the patient-course. Each course where the patient receives the agent or where a protocol-specific toxicity event is observed will be considered in the analysis. We will assume a beta prior distribution with  $\alpha = 0.6$  and  $\beta = 1.4$  and an unacceptable toxicity rate of  $p_0 = 30\%$ . At least once per month, we will calculate the posterior probability (given the data) that the probability of protocol-specific toxicity exceeds the 30% threshold, *i.e.*,  $P(p > 0.3 | \text{Data})$ . If there is a posterior probability of 80% that the toxicity rate is at least 30%, then accrual will be suspended pending review by DSMC. Examples of situations in which this rule will indicate protocol-specific toxicities have been noted and are presented below:

Number of failures	Number of patient-cycles
2	3
3	6
4	8
5	11
6	14
7	17
8	20
9	23
10	26
11	29
12	32
13	35
14	38

Interim monitoring will also be performed to watch for a 20% progression rate at week 10 in newly-diagnosed patients and a 40% progression rate at week 10 for relapsed and refractory patients. For newly-diagnosed patients, the beta parameters will be  $\alpha = 0.52$  and  $\beta = 2.08$ ; and for relapsed and refractory patients the beta parameters will be  $\alpha = 1.04$  and  $\beta = 1.56$ ; if there is a posterior probability of 80% that the progression rate at week 10 is at least 20% for newly-diagnosed patients or 40% for relapsed/refractory patients, then accrual for the respective cohort or cohorts will be suspended pending review by the DSMC. The stopping rule will be triggered as described in the following table:

Number of failures	Number of newly-diagnosed patients	Number of relapsed/refractory patients
2	4	2
3	8	4
4	12	6
5	16	8

6	20	11
7	24	13
8	29	15
9	33	17
10	38	19

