**Table 4 Acute GvHD, Chronic GvHD, and Overlap Syndrome**

Category	Time of Symptoms after HCT or DLI	Presence of Acute GvHD features	Presence of Chronic GvHD features
Acute GvHD			
Classic acute GvHD	≤100 d	Yes	No
Persistent, recurrent, or late-onset acute GvHD	>100 d	Yes	No
Chronic GvHD			
Classic chronic GvHD	No time limit	No	Yes
Overlap syndrome	No time limit	Yes	Yes

- Scoring of acute GvHD may need to occur past day 100. In particular, patients should continue to be scored for acute GvHD when classic acute GvHD symptoms (maculopapular rash, nausea, vomiting, anorexia, profuse diarrhea - particularly if bloody and ileus) persist past day 100 or if identical symptoms previously scored as acute GvHD resolve and then recur within 30 days during immunosuppression taper but past day 100.
- Those patients being scored as having acute GvHD should NOT have diagnostic or distinctive signs of chronic GvHD.
- Patients with both acute and chronic symptoms should be diagnosed as having Overlap Syndrome and scored according to their chronic GvHD score.**

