#### 2.0 Assessment of Liver GvHD

##### 2.1 Assessing for the Presence or Absence of Liver GvHD

- Hyperbilirubinemia (total bilirubin  $\geq 2.0$  mg/dL) in the **absence** of other signs of acute GvHD in the skin or GI tract:
  - Day 0-35: If hyperbilirubinemia alone is present with no other signs of acute GvHD in other organ systems, acute GvHD will not be diagnosed based solely on laboratory abnormalities. Acute GvHD will be diagnosed if findings on histopathology studies of liver from a biopsy or autopsy are confirmatory.
  - Day 35-100: If hyperbilirubinemia (must be conjugated bilirubin) is not improving or is exacerbated (especially if serum alkaline phosphatase is increased), in the absence of acute GvHD in other organ systems, no other etiologies are identified, and does not improve with discontinuation of hepatotoxic drugs, acute GvHD will be diagnosed. However, it is distinctly unusual to develop ascites or a coagulopathy in the early stages

of acute GvHD of the liver alone. In the absence of histopathology studies of liver from a biopsy or autopsy specimen, ascites or a coagulopathy secondary to liver dysfunction will be considered to indicate the presence of another disease process (e.g. veno-occlusive disease). Recommended non-invasive studies to define an etiology for hyperbilirubinemia are:

- a. Imaging of liver (CT or ultrasound)
- b. Hepatitis screen (only if ALT is elevated)
- c. PT
- d. Blood cultures
- e. Review of medication list for potentially hepatotoxic drugs
- f. Review of risk factors for viral liver infection (HSV, CMV, VZV, adenovirus, EBV, HBV, and HCV)
- g. Hemolysis screen

B. Pre-existing hyperbilirubinemia clearly attributed to an etiology other than acute GvHD in the presence of signs of acute GvHD in other organ systems.

- i) If pre-existing non-GvHD liver disease (documented clinically, by lab assessment, or by imaging studies) is stable or improving at the onset of signs of acute GvHD in other organs, then acute GvHD of the liver will not be considered to be present unless proven by liver biopsy or autopsy.
- ii) If hyperbilirubinemia worsens several days before or at the time of onset of signs of acute GvHD in other organ systems, GvHD will be considered to be present unless histopathology studies of liver are available and negative on a biopsy during that time interval or autopsy results exclude GvHD.

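### GvHD arising after protocol therapy ends (Day 42 for one-course patients) cannot trigger the automatic suspension rule, although the cited GvHD standard scores acute disease to Day 100 and beyond

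*Combined protocol and SAP*

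**What the plan says.** Section 9.3 lists the protocol-specific toxicities for real-time monitoring. Allograft failure and rejection have their own any-event rule. The Bayesian rule by patient-course covers "cytokine release syndrome grade 3 or higher, and graft versus host disease", with a pointer to Appendix V. On what enters the count, 9.3 says: "Each course where the patient receives the agent or where a protocol-specific toxicity event is observed will be considered in the analysis".

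Section 9.5 sets the window. A toxicity-evaluable patient is "considered in the analysis during the interval from study enrollment until protocol therapy is terminated" or a toxicity event is observed, whichever is first.

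Section 7.1.2 fixes the end of therapy: "End of therapy is Day 42 of Course LMP-TC1 for patients with a CR or PD after this course", and likewise for patients with PR or SD who have no product for a second course. Then: "End of therapy is Day 42 of Course LMP-TC2 for all other patients". The second course starts "no later than 21 days from the end of LMP-TC1" (section 4.4.5).

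Appendix V treats classic acute GvHD as occurring up to 100 days after HCT or DLI, has a category for later onset, and notes under Table 4: "Scoring of acute GvHD may need to occur past day 100". For raised bilirubin alone on Days 0-35, "acute GvHD will not be diagnosed based solely on laboratory abnormalities" unless histology confirms it. Table 2 allows such cases to be staged without biopsy on Days 36-100 if no other cause is found.

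**The concern.** The suspension rule and the standard it cites for GvHD use different time frames. The rule stops looking 35 days after the last infusion, or sooner for a patient taken off therapy early. The standard keeps scoring acute disease for about two further months. A completed course stays in the denominator, while an event from that course that appears after therapy ends is not added to the numerator. GvHD is one of the T-cell risks the trial chose to monitor by formula, and the rule could stay silent because of when an event appeared and not because of whether it occurred.

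**Working it through.** **1. The plan's own boundary.** Inputs from 9.3: prior Beta(0.6, 1.4), limit 30%, posterior threshold 80%. With x events in n patient-courses the posterior is Beta(0.6 + x, 1.4 + n - x), and the rule fires if P(p > 0.30) is at least 0.80. For 2 events, n = 3 gives 0.838 and n = 4 gives 0.734, so the boundary is 2/3. For 14 events, n = 38 gives 0.801 and n = 39 gives 0.769, so it is 14/38. All 13 rows of the table reproduce. The arithmetic of the rule is correct; the question is which events feed it.

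**2. Length of the window.** Infusions are on Days 0 and 7 of each course (4.4.3, 4.5.3).
- One course: from the last infusion to the end of the count, 42 - 7 = 35 days. Days 43-100 from the first infusion (58 days) lie outside.
- Two courses, from the first infusion: 42 + (0 to 21) + 42 = 84 to 105 days. From the last infusion: again 35 days.

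**3. Isolated liver GvHD without biopsy.** If the Appendix V days are counted from the first infusion, a one-course patient can contribute such an event only on Days 36-42, which is 7 of the 65 days from 36 to 100. If they are counted from the last infusion, the count closes on Day 35 and none of the 65 days is covered. The documents do not say which infusion starts the clock. This applies only to that one presentation.

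**4. What one uncounted event does.** At a boundary, moving one event out of the count while keeping its course gives:

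| Events/courses | Posterior | One event uncounted |
|---|---|---|
| 2/3 | 0.838 | 0.490 |
| 5/11 | 0.829 | 0.638 |
| 14/38 | 0.801 | 0.694 |

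The same holds at all 13 boundaries: one lost event removes the trigger.

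**5. Illustration, with truncation restricted to GvHD.** The documents give no GvHD rate or onset distribution, so everything here is assumed. Half of the monitored events are CRS and are counted in full, because CRS is early. A share c of the GvHD events falls inside the window, and c = 0.42 corresponds to uniform onset over Days 0-100 in one-course patients. The counted rate is then p x (0.5 + 0.5c). The chance that the rule fires within 30 courses, checked after each course, is:

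| True rate p | All counted | c = 0.60 | c = 0.42 |
|---|---|---|---|
| 40% | 82% | 57% (counted rate 32%) | 44% (28.4%) |
| 30% | 50% | 30% (24%) | 22% (21.3%) |
| 4% | 0.5% | lower still | lower still |

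The table still overstates the loss, because it truncates every course, including first courses of patients who go on to a second and remain in the window.

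**The case against.** A reader might infer that late GvHD is invisible, or that the posterior rule is the only route to the DSMC. The documents do not support that. Patients off therapy are still followed (8.1), all GvHD grades go to routine reporting with no stated cut-off (11.12), and Grade 3 and higher is expedited (11.10). Related serious events more than 30 days after the last dose are reportable (11.4.1). The DSMC reviews toxicity reports, and the study committee and statistician can ask it to look (12.2). What is missing is the automatic trigger only.

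A reader might also shrink the whole event rate to 42% and conclude that at a true 40% rate the rule fires 12% of the time instead of 82% (6% instead of 50% at a true 30%). That treats early CRS as if it were late GvHD. Rates of 30-40% also sit badly with the background: no GvHD in the third-party phase 2 series (2.5.4), 2 of 50 recipients with Grade I de novo GvHD after third-party virus-specific cells (2.5.5), and no de novo acute GvHD in 153 recipients of donor-derived cells (2.5.6). At 4% (2/50) the rule almost never fires even with every event counted.

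Appendix V is a transplant guideline whose Day 100 clock runs from HCT or DLI, and 9.3 cites it without adopting a 100-day observation period. An on-therapy window could be a deliberate choice. Skin disease, biopsy-proven disease, and liver disease accompanying skin or GI disease can also be staged earlier.

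These points limit the size and the wording of the concern. They do not remove the gap: no passage adds a post-therapy event to the count. The phrase in 9.3 about courses where an event is observed could be read more broadly, but it counts courses, and none is open once therapy has ended. A suspension rule should not rest on that ambiguity.

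**Conclusion.** The gap is real but narrow. On the text, GvHD that first appears after protocol therapy ends cannot fire the Bayesian suspension rule. The cut-off comes 35 days after the last infusion for one-course and two-course patients alike, and earlier for those removed early. The direction is certain: late events leave the numerator while their courses stay in the denominator. The size is not known, because it depends on a GvHD rate and onset timing that the documents do not give, and the background suggests a low rate. The firing probabilities above illustrate the mechanism and are not estimates for this trial. The case for the change rests on consistency between the rule and its cited standard, and on low cost, not on evidence that the rule would fail in practice.

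A longer window alone would not be enough. Section 9.5 defines the event as a related death on therapy or a dose-limiting toxicity, a term the protocol does not define, and this does not match the CRS and GvHD list in 9.3. Section 10.2.4.1 gives a different definition of who is evaluable for toxicity.

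**What to change.** - **9.3 and 9.5:** count GvHD (Appendix V) in the suspension rule through Day 100 after the last LMP-specific T-cell infusion, whether or not protocol therapy has ended. State that the clock starts at the last infusion, since Appendix V counts from HCT or DLI.
- **Numerator and denominator:** assign a late event to the last LMP-TC course received. Let courses enter the denominator as now, and update the numerator when a late event is reported.
- **11.12:** state the same end date for routine GvHD reporting.
- **Definitions:** reconcile the 9.5 event definition and the evaluability text in 10.2.4.1 with the CRS and GvHD list in 9.3, and define or remove the dose-limiting toxicity term.

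**Cost.** Protocol wording and a GvHD field on existing follow-up forms. The boundary table does not change. The Month 1, 2 and 3 visits in 7.1.3 already collect history, examination and bilirubin. For a patient who ends therapy on Day 42, Month 3 falls about 35 + 90 = 125 days after the last infusion, so no new visit is needed. A patient removed within about 10 days of an infusion would reach Month 3 slightly before Day 100, and the remaining days would rely on ongoing all-grade reporting.

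**Downsides.** Attribution is harder once off-protocol chemotherapy has started. Day 100 after the last infusion is course Day 107, or 107 - 42 = 65 days after the present cut-off, so recent courses will have incomplete GvHD follow-up at each monthly look. The monitoring report should show how many.

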#### 9.6 Gender and Minority Accrual Estimates

The gender and minority distribution of the study population is expected to be:

Racial Categories	Ethnic Categories				Total	
	Not Hispanic or Latino		Hispanic or Latino			
	Female	Male	Female	Male		
American Indian/ Alaska Native	0	1	0	0	1	
Asian	0	0	0	0	0	
Native Hawaiian or Other Pacific Islander	0	0	0	0	0	
Black or African American	7	3	0	0	10	
White	16	32	3	3	54	
More Than One Race	0	0	0	0	0	
Total	23	36	3	3	65	

INTERNATIONAL (including Canadian participants) PLANNED ENROLLMENT REPORT						
Racial Categories	Ethnic Categories				Total	
	Not Hispanic or Latino		Hispanic or Latino			
	Female	Male	Female	Male		
American Indian/ Alaska Native	0	1	0	0	1	
Asian	0	0	0	0	0	
Native Hawaiian or Other Pacific Islander	0	0	0	0	0	
Black or African American	3	1	0	0	4	
White	6	12	1	1	20	
More Than One Race	0	0	0	0	0	
Total	9	14	1	1	25	

This distribution was derived from patients enrolled on ANHL0221, the most recent COG study of PTLD.

#### 9.7 Correlative Studies

We will summarize the *in vivo* measurements of virus-specific T cells over the pre-LMP-specific T cells to the post-LMP-specific T cells monitoring period in patients who receive LMP-specific T cells versus patients who do not to assess the pattern and magnitude of T-cell expansion and persistence for EBV and response to LMP-specific T cells administration using plots generated for each patient to graphically illustrate the pattern and duration of LMP-specific T-cell persistence and expansion. The area under the curve (AUC) will be calculated for each subject by the trapezoidal rule. The AUCs will be summarized, and after logarithmic transformation, will be analyzed by a two-sample *t*-test. Measurements of immunity, tetramer analysis and functional assays will be evaluated by descriptive statistics (means, standard deviations, medians and ranges) at each time point and analyzed by paired *t*-tests to compare changes from pre- to post-infusion.

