##### 4.1.2.1 **Arm RTX**

**Cohort A:** Newly diagnosed patients who achieve a complete response (CR) after Induction will be assigned to Arm RTX to receive a second 21-day course of rituximab or biosimilar (Course RTX2).

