##### 4.1.2.2 **Arm LMP-TC**

**Cohort A:** Newly diagnosed patients who do not achieve a complete response (CR) after Induction will be assigned to Arm LMP-TC.

**Cohort B:** All relapsed patients will be assigned to Arm LMP-TC after induction regardless of response.

**Cohort C:** All patients with refractory disease who have received rituximab (or biosimilar) within 90 days according to institutional guidelines are assigned to Cohort C and proceed directly to Arm LMP-

TC at enrollment.

Patients assigned to Arm LMP-TC without a suitable LMP-specific T-cell product will go off protocol therapy. Further treatment with chemotherapy is at the discretion of the treating physician.

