#### 9.4 Evaluability for Response

Eligible patients assigned to Arm LMP-TC will be considered evaluable for the primary endpoint (percentage successfully matched and treated). All 3 Cohorts will be combined into a single set of patients for the analysis.

All eligible patients will be evaluable for Aims 1.2.1, 1.2.8, and 1.3.2. For Aim 1.2.1, all patients who submit HLA typing by the end of the trial will be evaluable, regardless of the timing of the submission.

Any eligible patient who receives at least one dose of RTX will be considered evaluable for Aims 1.2.2–1.2.4 and 1.2.6.

Any eligible patient who receives at least one dose of LMP-specific T cells will be considered evaluable for Aims 1.2.5, 1.2.7, 1.3.1, and 1.3.3.

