##### A. General Immune reconstitution

*Hypothesis and Rationale:* Third Party LMP-specific T cells in combination with rituximab will be superior in aiding the immune reconstitution of the recipients compared to rituximab alone. The rationale behind this correlative study is that EBV positive PTLD is caused by a defective immune system and LMP-specific T cells lead to EBV specific immune reconstitution. Monitoring occurrence and persistence of this immune reconstitution may be able to predict response and/or risk of recurrence of PTLD. Studies to evaluate general immune reconstitution will include:

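### The two-group T-cell AUC test in Section 9.7 compares arms defined by cohort and response, so its p-value cannot be read as an LMP-TC effect; Sections 9.4, 9.7 and Appendix IV also disagree on who is compared

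*Combined protocol and SAP*

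**What the plan says.** - **The comparison.** Section 9.7 sets measurements "in patients who receive LMP-specific T cells versus patients who do not" side by side. AUC is computed by the trapezoidal rule, and then: "The AUCs will be summarized, and after logarithmic transformation, will be analyzed by a two-sample" t-test. It gives no covariates, time window, alpha, sample size or named aim. The same section plans per-patient plots, descriptive summaries and paired pre/post-infusion tests.
- **Arm assignment.** Section 4.1.2.1: "Newly diagnosed patients who achieve a complete response (CR) after Induction will be assigned to Arm RTX". Section 4.1.2.2: "Newly diagnosed patients who do not achieve a complete response (CR) after Induction will be assigned to Arm LMP-TC", and for Cohort B: "All relapsed patients will be assigned to Arm LMP-TC after induction regardless of response". All Cohort C (refractory) patients go directly to Arm LMP-TC.
- **Evaluability.** Section 9.4: "Any eligible patient who receives at least one dose of LMP-specific T cells will be considered evaluable for Aims 1.2.5, 1.2.7, 1.3.1, and 1.3.3". All eligible patients are evaluable for Aim 1.3.2.
- **Hypothesis.** Appendix IV, part A: "Third Party LMP-specific T cells in combination with rituximab will be superior in aiding the immune reconstitution of the recipients compared to rituximab alone". Appendix IV.4 refers to Section 9.7 for the statistics of all the correlative studies.
- **Sampling.** Sections 15.1.2 and 15.1.3 schedule T-cell samples from RTX2 Day 1 or LMP-TC1 Day 0. The overview table in Section 7.2 shows none during Induction.

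**The concern.** A two-sample t-test gives an interpretable treatment p-value only if the groups would have had similar AUCs without the treatment. Here, group membership is decided by cohort and by response to rituximab. The protocol's background links these features to the outcome. Section 2.6 reports a rise in EBV-specific T-cell frequency in responders to T-cell therapy. Section 2.7 describes an inverse relation between viremia and EBV-specific T cells, but also strong T-cell expansion in response to viremia. It adds that reducing immunosuppression leads to autologous EBV-specific reconstitution. The bias could therefore run either way.

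At stake is a between-group p-value that could be reported as evidence for or against a T-cell effect on immune reconstitution when it mixes that effect with selection. In addition, an analyst following 9.4 and one following 9.7 would build different analysis sets.

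**Working it through.** The documents give no sample size, effect size or power for this test, so there is no planned figure to reproduce. The check is mainly structural.

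**1. Who can contribute an AUC**

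| Patient group | Assigned arm | Scheduled T-cell samples |
|---|---|---|
| Cohort A, CR after RTX1 | RTX | From RTX2 Day 1 |
| Cohort A, not in CR | LMP-TC | From LMP-TC1 Day 0 |
| Cohort B, any response | LMP-TC | From LMP-TC1 Day 0 |
| Cohort C | LMP-TC | From LMP-TC1 Day 0 |
| Assigned LMP-TC, no product | Off protocol therapy | None (no Day 0 exists) |

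The wording of 9.7 would admit the last row as non-recipients, but the Section 15 schedule gives them no T-cell samples. The comparators with a planned AUC are thus the first row: newly diagnosed and in CR. No patient in that joint category is assigned T cells.

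**2. Other differences between the two AUCs**

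- Sampling days (15.1.3): RTX2 Days 1, 8, 15, 21 and Weeks 6 and 8; LMP-TC1 Days 0, 7, 14, 28, 41 and Week 8.
- Follow-up length: the general-reconstitution samples (15.1.2) run to Month 12 and the persistence samples (15.1.3) to Week 8. Section 9.7 sets no window, and an AUC grows with time observed.
- Treatment during the window: Arm RTX patients receive three more rituximab doses.
- Immunosuppression: numeric minimum levels are required on Arm LMP-TC (4.4.5); none is stated for Arm RTX.
- Infused cells: recipients' counts include third-party cells, and the visible tetramer and ELISPOT descriptions in Appendix IV do not say how these are separated from the recipient's own.

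**3. Likely comparator number**

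If *k* of the 30 LMP-TC patients come from Cohort A, and a share *c* of Cohort A reaches CR, the expected Arm RTX number is *k* × *c*/(1 − *c*).

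- Section 9.1 assumes 40% of Cohort A goes to LMP-TC, so *c* = 0.60 and the factor is 0.6/0.4 = 1.5. For *k* = 10, 20, 30 this gives 15, 30, 45.
- Section 2.4.2 reports 14 patients in CR after three rituximab doses in the German trial. If the denominator is the 49 in Table 1 (an assumption), the factor is 14/35 = 0.4, giving 4, 8, 12.

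Optional consent lowers these numbers. A larger group does not reduce the bias.

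**4. What an offset would do (illustration only)**

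Assume no T-cell effect, a two-sided 5% test, 24 recipients, and groups differing by *d* SD in log AUC through selection alone. The rejection probability is that of a noncentral t with n₁ + n₂ − 2 degrees of freedom and noncentrality *d*·√(n₁n₂/(n₁+n₂)). For *d* = 0.5 with 24 and 30 patients, this is 0.5 × √(720/54) = 1.83.

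| Recipients / comparators | d = 0 | d = 0.25 | d = 0.5 | d = 0.8 |
|---|---|---|---|---|
| 24 / 45 | 0.05 | 0.16 | 0.50 | 0.88 |
| 24 / 30 | 0.05 | 0.15 | 0.43 | 0.82 |
| 24 / 15 | 0.05 | 0.12 | 0.32 | 0.66 |

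The documents supply neither *d* nor the 24. The table shows only that a modest offset is enough to make the p-value misleading.

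**5. Evaluability**

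If the AUC test serves Aim 1.3.1, applying 9.4 leaves no comparators. If it serves Aim 1.3.2, all eligible patients are evaluable, but that aim concerns the correlation of viremia with T cells and not a recipient/non-recipient contrast. Section 9.7 does not say which applies.

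**The case against.** The strongest reply is that this is an exploratory analysis on optional samples, tested as funding allows, and that no endpoint, stopping rule or treatment assignment uses it. That stands, and it limits the weight of the point. Five stronger readings are tempting but are not supported:

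- *The groups share no overlap on anything.* Cohort B patients in CR also receive T cells, and newly diagnosed patients appear in both arms. Only the joint newly-diagnosed-and-CR category lacks overlap. An additive adjustment for cohort and response could be fitted, but it would rest on the unverifiable assumption that the two effects do not interact, and 9.7 plans none.
- *The comparator set is empty, so the test cannot be run.* That follows only if the test serves Aim 1.3.1, which 9.7 does not say; 9.7 itself names a comparator. It is a conflict between sections and not a proven impossibility.
- *The superiority hypothesis is formally tested by this AUC.* The hypothesis sits under general immune reconstitution (immunophenotyping and cytokines), whereas virus-specific T cells belong more naturally to part B of Appendix IV. The link through IV.4, and through possible gating on EBV tetramer-positive cells in part A, is plausible but not stated.
- *Further development hangs on this p-value.* Section 2.9 and Appendix IV.1 tie development to finding autologous reconstitution without persistence, and name no test. Section 2.2 looks to future randomised studies.
- *Arm RTX immunosuppression is unmanaged.* Section 4.3.2 has levels checked where applicable and adjusted when subtherapeutic. The difference is the numeric minimum.

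It is also fair to say that the paired analysis already in 9.7 does not by itself answer Aim 1.3.1. It has no control, and the change includes infused cells.

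**Conclusion.** The concern holds in a limited form. As planned, the log-AUC p-value cannot be read as a T-cell effect, because the comparators with scheduled samples are newly diagnosed patients in CR and no such patient is assigned T cells. Different sampling days, different immunosuppression requirements and the presence of infused cells add to this. Separately, 9.4 conflicts with 9.7 and with Appendix IV over whether Aim 1.3.1 has a comparison group.

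This conclusion rests on the assignment rules in 4.1.2 and the schedule in Section 15; it needs no numerical assumption. The size and direction of the bias are unknown, and the rejection rates above depend on assumed offsets and numbers. The consequence is confined to an exploratory aim. The primary feasibility endpoint and the secondary endpoints are unaffected.

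**What to change.** 1. **Section 9.7, between-group contrast.** Report Arm RTX versus LMP-TC AUCs as estimates and curves without a hypothesis test, labelled non-randomised and confounded by response and cohort. Name the aim it serves.
2. **Section 9.7, AUC definition.** Compute AUC over the common window from Day 0 (LMP-TC1) or Day 1 (RTX2) to Week 8, divided by time observed. Since Section 4.5.1 notes that Week 8 is likely to fall within Course LMP-TC2 for patients who continue, flag Week 8 values taken after a further infusion.
3. **Aim 1.3.1.** Use the within-patient change from LMP-TC1 Day 0 (log scale, paired, already in 9.7). Report it as an uncontrolled change in total EBV-specific T cells, and not as autologous reconstitution unless the assay separates recipient from third-party cells.
4. **Section 9.4 and Appendix IV.** Make the evaluable set match the analysis in 9.7: recipients for the paired change, with Arm RTX patients added for the descriptive contrast. Reword the superiority hypothesis, which this design cannot test.

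The cost is wording changes only, with no new patients or samples. The loss is one exploratory between-group p-value.
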